**FLE-002 (INSTANT) – Final Analysis****Statistical Analysis Plan**

-If Core Laboratory did not report Conversion of AF to SR, then the investigator reported information is used for the period for which no Core Laboratory information is available.

-If Core Laboratory reported Conversion of AF to SR, then the investigator reported information is not used. Subject already converted within the period analyzed by Core Laboratory.

These rules will be followed for *recurrence of AF*:

-If Core Laboratory did not report Recurrence of AF, then the investigator reported information is used for the period for which no Core Laboratory information is available.

-If Core Laboratory reported Recurrence of AF, then the investigator reported information is not used. This applies for recurrences during the Holter or TTM monitoring period. If AF recurrence occurs outside of the monitoring period but prior to Day 5, the event will be entered in the EDC as a recurrent AF episode by the investigator.

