#### 7.2.5 Imputation of Missing Data

##### Imputation of date and time values

Date and time values will only be imputed if the missing value impacts the reporting of Adverse Events, Conversion of AF to SR or recurrence of AF:

- For adverse events or recurrence of AF, the earliest possible date or time will be imputed.  
*Example: For AEs occurring after initiation of study medication for which the start time of the AE is missing, the time of initiation of study medication will be imputed to be the start time of the AE*
- In conversion from AF to SR, the last possible date or time will be imputed.  
*Example: If conversion to SR is known to have occurred between initiation of study medication and 60 minutes post initiation of study medication, but the time of conversion to SR is unknown: 60 minutes post initiation of study drug is imputed for time of conversion to SR.*
- For Treatment Emergent Adverse Events: a worst-case approach is used. If AE can be Treatment Emergent, event is assumed to be Treatment Emergent.  
For instance: if medication started at 12h:12m:45s and Adverse Event started at 12h:12m (seconds unknown) event is assumed to be Treatment Emergent

**FLE-002 (INSTANT) – Final Analysis****Statistical Analysis Plan****Conversion of AF to SR and recurrence of AF: frequency analysis.**

No missing information is expected: if Core Laboratory analysis is missing or incomplete, then investigator reported information is available (refer to section 6 SAP) for analysis. Should however information regarding the status of conversion to SR or recurrence of AF be incomplete, then the subject is assumed to be free of the event between time of last available information and the end of the reported period.

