## FLE-002 (INSTANT) – Final Analysis

## Statistical Analysis Plan

Analysis is performed for the mITT population. A Subject meets the endpoint if conversion occurred within 90 minutes after initiation of dosing without the use alternative medication (e.g., IV flecainide and propafenone) or procedures (e.g., ECV). If a subject's conversion status is unknown, then the analysis will assume that the subject did not convert.

The percentage is calculated as:

$$p = 100 * (\text{number of converted subjects} / \text{number of subjects in mITT population})$$

A 90% exact binomial confidence interval will be calculated for the percentage.

No formal testing will take place. Analysis will not be performed for the PLS population.

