**FLE-002 (INSTANT) – Final Analysis****Statistical Analysis Plan**

This endpoint is derived from the primary efficacy endpoint at 90 minutes after initiation of dosing. The endpoint is met if the subject's AF converts to SR within 90 minutes after initiation of dosing without an alternative therapy and without subsequent AF recurrence up to discharge requiring additional intervention, either by electrical or pharmacological cardioversion or by rate control treatments.

This proportion of subjects that convert to SR without AF recurrence is estimated as the number of subjects who meet the endpoint, divided by the total number of mITT subjects. The estimate for the proportion and its associated 95% Clopper-Pearson CI will be derived.

The requirements for meeting the endpoint are thus as follows:

*- the start time of the conversion of AF to SR is within 90 minutes (including 90 minutes) after the initiation of study drug, AND EITHER*

*-no recurrence of AF occurred between time of conversion and discharge, OR  
-recurrence of AF occurred between time of conversion and discharge but for subject none of the indicated interventions (as reported by investigator) was started between initiation of dosing and discharge.*

Discharge is left to the discretion of the treating physician 90 minutes post dose (-10 minute window).

Additionally, analysis is repeated for the proportion of subjects whose AF converted to SR within 90 minutes post dose.

*No imputation will take place, i.e., the subject is assumed to be free of event (No Conversion, No AF Recurrence, None of the three Interventions) after the time last information is available.*

Analysis will not be performed for the PLS population.

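### In the durable-conversion endpoint, a converter whose recurrence and intervention status up to discharge is unknown is scored as a success, although the SAP says nothing is imputed

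*SAP*

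**What the plan says.** SAP 9.2.2.7 defines a secondary endpoint: conversion within 90 minutes of starting dosing, without a later AF recurrence that leads to electrical cardioversion, pharmacological cardioversion or rate control before discharge. A converter can satisfy the second part in two ways. The first is "no recurrence of AF occurred between time of conversion and discharge, OR" and the second is a recurrence with none of the interventions started. The count is "divided by the total number of mITT subjects", and "The estimate for the proportion and its associated 95% Clopper-Pearson CI will be derived".

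The section then says that no imputation is done and, in the same sentence, that anyone without later data will be "assumed to be free of event (No Conversion, No AF Recurrence, None of the three Interventions) after the time last information is available".

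Three other SAP passages bear on this:

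- Section 9.2.1, primary endpoint: "If a subject's conversion status is unknown, then the analysis will assume that the subject did not convert".
- Section 7.2.5, frequency analysis of conversion and recurrence: if status is incomplete, "then the subject is assumed to be free of the event between time of last available information and the end of the reported period". The same section states: "No missing information is expected: if Core Laboratory analysis is missing or incomplete, then investigator reported information is available".
- Section 6, partly missing Core Laboratory data: "If Core Laboratory did not report Recurrence of AF, then the investigator reported information is used for the period" that the Core Laboratory did not cover.

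Protocol 10.2.1.8 B defines the endpoint but gives no missing-data rule for it.

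**The concern.** Assuming that an event did not happen is cautious when the event is conversion and favourable when it is recurrence or rescue. SAP 9.2.2.7 applies the assumption to both. A converter whose data stop before discharge, with no failure recorded up to then, stays in the denominator and enters the numerator. That is a single favourable imputation, whatever the sentence calls it.

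The endpoint is meant to show that conversion lasts until the subject leaves the hospital. The trial has no concurrent control, and SAP 7.2.5 plans no sensitivity analysis for missing values. Nothing requires the report to say how many successes rest on the assumption, so a reader could not separate observed from assumed durability.

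**Working it through.** The plan states no figure for this endpoint, so there is none to reproduce. The check has two parts: how the rule scores each case, and how much one subject can move the estimate.

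**1. Scoring under SAP 9.2.2.7**

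| What is missing | Assumption | Score |
|---|---|---|
| Conversion status | Not converted | Failure, as in 9.2.1 |
| Recurrence status after conversion | No recurrence | Success |
| Intervention status after conversion | No intervention | Success |

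Only the last two rows are favourable, and they apply only to converters.

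**2. Comparison with the SAP's other rules**

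- Recurrence with a missing date or time (7.2.5): the earliest possible time is used.
- Conversion with a missing date or time (7.2.5): the last possible time is used.
- Day 2, Day 5 and symptom endpoints (9.2.2.3 to 9.2.2.6 and 9.2.2.8): subjects without data leave the denominator.

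Among these, only the rule for recurrence and intervention after conversion turns missing data into success. It appears in 9.2.2.7 and, for recurrence, in general form in 7.2.5.

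**3. Size**

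Let N be the mITT cohort size, c the converters, m the converters with unestablished status up to discharge, and k those among the m who truly recurred and were treated (0 ≤ k ≤ m). Assume no other failures after conversion.

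- SAP rule: c/N, whatever m is.
- Missing counted as failure: (c − m)/N.
- Difference between the rules: m/N.
- Actual inflation under the SAP rule: k/N, which is at most m/N.

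Inputs: 13 of 27 converted in the Part A 120 mg FlecIH-103 cohort (Protocol 1.4), and Part B planned 25 mITT subjects (Protocol 10.3 B). The assumed pooled N before Part C is 27 + 25 = 52. Taking 12 of 25 (48%) in Part B as an assumption gives c = 13 + 12 = 25. The values of m are also assumptions, because the documents give no rate of missing data.

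Per subject: 1/27 = 3.7 points; 1/52 = 1.9 points.

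| m | N = 27, c = 13: missing = failure (95% Clopper-Pearson) | N = 52, c = 25: missing = failure (95% Clopper-Pearson) |
|---|---|---|
| 0 | 48.1% (28.7 to 68.1) | 48.1% (34.0 to 62.4) |
| 1 | 44.4% (25.5 to 64.7) | 46.2% (32.2 to 60.5) |
| 2 | 40.7% (22.4 to 61.2) | 44.2% (30.5 to 58.7) |
| 3 | 37.0% (19.4 to 57.6) | 42.3% (28.7 to 56.8) |

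The SAP rule gives the m = 0 row whatever m is. N = 27 is an illustration, since Part A alone is not one of the four cohorts in SAP Table 1. Adding Part C lowers the pooled per-subject effect below 1.9 points. The documents do not give the sizes of the Part C cohort or of the two cohorts split by predose flecainide; 1/N is larger in a smaller cohort.

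**The case against.** The strongest reply is that the rule will hardly ever operate. The window is short. Subjects are on telemetry and Holter to 90 minutes post dose. Gaps in the Core Laboratory analysis are filled from investigator reports, and SAP section 6 has investigators enter recurrences that fall outside the monitoring period. Interventions before discharge take place on site and are investigator-reported. A converter fails only if a recurrence and an intervention both occurred, so missing rhythm data alone conceal no failure. The endpoint is secondary, and the final analysis has no formal testing (SAP 6.2 and 7.1), so no type I error is affected.

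All of this stands, and it limits the size of the point. It does not change the direction of the rule. The SAP itself foresees partial Core Laboratory records, with an example analysed to only 28 of the planned 90 minutes. Discharge is at the physician's discretion and may come after the Holter ends (Protocol 6.3.1 B and 7.1 B). If the rule never operates, reporting a count of zero costs nothing.

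A reader might infer more than the documents support:

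- **That missing data can only raise this rate.** Missing conversion status lowers it, because that subject counts as a failure.
- **That the SAP adopts a rule opposite to the primary endpoint's.** The rule is worded the same way for both events; only its effect differs.
- **That every shortened Holter record adds a false success.** Investigator data come first, and m/N is the distance to a worst-case rule, not a measured bias.
- **That the effect should be read at Part B's 25 subjects or per converter.** Part B alone is not a cohort in this SAP, and the denominator is all mITT subjects.

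**Conclusion.** The point holds in a limited form. In SAP 9.2.2.7, a converter whose status up to discharge is established by neither the Core Laboratory nor the investigator is scored as a success, and the text wrongly describes this as no imputation. Compared with missing = failure, each such converter adds 1/N: about 3.7 points at N = 27, and about 1.9 at the assumed pooled N of 52, less once Part C is included. True inflation is at most that, and arises only if the subject both recurred and was treated. The number affected is not given, is probably small and may be zero. The point estimate and its 95% interval are affected; no test is. It deserves correction because the endpoint is the plan's evidence that conversion lasts to discharge and the assumption would otherwise go unseen.

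**What to change.** In SAP 9.2.2.7:

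1. Delete the statement that no imputation takes place.
2. Score a converter as not meeting the endpoint when neither Core Laboratory nor investigator data on rhythm and intervention establish status up to discharge.
3. Define when status is established. The end of Holter recording at 90 minutes post dose should not by itself count as incomplete; otherwise converters discharged later could be failed wrongly. A complete investigator record showing no intervention up to discharge is sufficient, because the endpoint is then met with or without a recurrence.
4. Keep the current rule as a sensitivity result, and report the number of converters affected in each cohort.
5. Align the recurrence part of SAP 7.2.5 for this endpoint.

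The cost is a few sentences of SAP text, one extra count and one extra row per cohort. The reported rate may be slightly less favourable; if no converter is affected, it does not change.

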**9.2.2.8 Proportion of subjects in SR on Day 5**

The Modified ITT Population will be used to determine the proportion of subjects in SR on Day 5 (second follow-up visit).

The rhythm status used for the evaluation of this secondary efficacy endpoint is derived from the remote ECG system, in which the subject's heart rhythm is recorded.

A subject is considered in SR on Day 5 if the subject's sinus rhythm during the recording is longer in duration (in seconds) than any of the other reported rhythms (refer to SAS section 5.2). The variable is set to missing if no evaluable remote ECG recording is available for analysis.

The proportion is estimated by the number of subjects in SR on Day 5, divided by the total number of subjects with available data.

The Modified ITT Population will be used to determine the proportion of subjects with reduced or no AF symptoms (compared to baseline) at discharge. Discharge is left to the discretion of the treating physician 90 minutes post dose (-10 minute window).

**FLE-002 (INSTANT) – Final Analysis****Statistical Analysis Plan**

Analysis will be performed for:

- the complete Modified ITT population
- mITT subjects whose AF converted to SR by inhaled flecainide within 90 minutes after initiation of dosing (subjects meeting the primary efficacy endpoint)
- mITT subjects whose AF was not converted to SR by inhaled flecainide within 90 minutes after initiation of dosing (subjects not meeting the primary efficacy endpoint)

Analysis will not be performed for the PLS population.

**9.2.2.9 Adverse Events**

Adverse events in the MLS will be reported for the Safety MLS population, meaning for subjects who started study medication, regardless of if subject was in AF when starting study medication.

Refer to SAP section 5.6.3. for the AE results reported for Part B and Part C MLS subjects, refer to SAP section 5.6.4 for the AE results reported for Part A subjects.

Adverse Events are coded as serious or non-serious, as related or not related to study medication, and as related or not related to study device. Adverse Events of Special Interest (AESI) and Serious Events of Special Interest (SAESI) are identified. Results are MedDRA coded (version 23.1 or higher).

In all tables the number of AEs, the number of subjects with at least one occurrence of the AE, and the percentage of subjects with at least one occurrence of the AE are reported by cohort (refer to SAP section 8.7).

*If subject information is not complete up to the end of the planned End of Study (i.e., subject is lost to follow-up), subject is assumed to be free of events up to planned End of Study.*

These results will be reported:

1. Any Adverse Event (AE)
  - overall
  - per combination of MedDRA System organ Class and MedDRA Preferred Term:
    - Any Event
    - Events occurring between IC and initiation of study medication
    - Events between study medication and 4 hours after initiation
    - Events between 4 hours after initiation and 24 hours after initiation
    - Events between 24 hours after initiation and end of observation period
2. Any Serious Adverse Event (SAE)
  - overall
  - per combination of MedDRA System organ Class and MedDRA Preferred Term:
    - Any Event
    - Events occurring between IC and initiation of study medication
    - Events between study medication and 4 hours after initiation
    - Events between 4 hours after initiation and 24 hours after initiation

## FLE-002 (INSTANT) – Final Analysis

## Statistical Analysis Plan

- Events between 24 hours after initiation and end of observation period
- Any Treatment Emergent Adverse Event (TEAE)
  - overall
  - per combination of MedDRA System organ Class and MedDRA Preferred Term:
  - Any Event
    - By severity
    - By relationship to study medication
    - TEAEs that are moderate or severe and related to study medication
- - Events between study medication and 4 hours after initiation
  - Events between 4 hours after initiation and 24 hours after initiation
  - Events between 24 hours after initiation and end of observation period

3. Any Treatment Emergent Serious Adverse Event (TESAE)

- overall
- per combination of MedDRA System organ Class and MedDRA Preferred Term:
- Any Event
- Events between study medication and 4 hours after initiation
- Events between 4 hours after initiation and 24 hours after initiation
- Events between 24 hours after initiation and end of observation period

The end of the extended observation period is defined as Visit 2 (Day 5). Subjects enrolled in Part A, Part B or Part C MLS who are also included in the Part C Patient-Led sub-study will be followed until a recurrent episode of AF is treated, or approximately 8 months after consent (whichever comes first); events starting after Visit 2 will not be included in the MLS part of the final statistical report but will be included in the PLS part of the final statistical report.

4. Adverse Events of Special Interest (AESI)

These results will be reported:

- Listing of AESI
- Overall number of AESI

Specification (per type of AESI, refer to SAP section 3.4)

AESI will be reported only if starting on or after initiation of study medication (Treatment Emergent).

The definition for AESI was modified during the trial based on examination of the data and regulatory interactions with the US FDA. All AESIs will be tabulated using a slightly adjusted definition compared to the Protocol version 8.0\EU-1 AESI definition, results are provided by sponsor (refer to SAP section 5.6.5 and Annex A); in the listings all results will be included: as per the Cardialysis Safety Team (Part A, refer to SAP section 5.6.2), investigator (Part B and C, refer to SAP section 5.6.1) and by Sponsor (Parts A, B and C, refer to SAP section 5.6.5 and Annex A). AESIs will be classified as Cardiovascular or non-Cardiovascular, refer to SAP section Annex A.

5. Serious Adverse Events of Special Interest (SAESI)

These results will be reported:

- Listing of SAESI

## FLE-002 (INSTANT) – Final Analysis

## Statistical Analysis Plan

### -Overall number of SAESI

SAESIs will be reported only if the event start time is on or after initiation of study medication (Treatment Emergent).

Only from Protocol version 8.0\EU-1 onwards SAESI was defined in study protocol. SAESI will be tabulated according to a slightly adjusted definition compared to the Protocol version 8.0\EU-1 SAESI definition, results are provided by Sponsor (refer to SAP section 5.6.5 and Annex A); in the listings all results will be included: as indicated by investigator and by Sponsor (Parts A, B and C, refer to SAP section 5.6.5 and Annex A).

SAESI will be classified as Cardiovascular or non-Cardiovascular, refer to SAP section Annex A.

### Reporting of AE

All Adverse Events will be included in listings. AE occurring in the PLS part of the study will be listed separately. Listings will include flags indicating:

- Is reported event Treatment Emergent?
- Are reported events categorized by investigator (Parts B and Part C MLS) or Cardialysis Safety Team (Part A) as 'AESI'?
- Are reported events categorized by investigator as 'Serious AESI'?
- Are reported events categorized by sponsor as 'AESI'? (refer to Appendix A SAP)
- Are reported events categorized by sponsor as 'Serious AESI'? (refer to Appendix A SAP)

Adverse events tables will be reported as follows:

- 1) All AEs from time of MLS consent through MLS Day 5
- 2) Treatment Emergent AEs from start of MLS dosing through MLS Day 5

Tables will thus exclude AE that start in the PLS part of the study.

No tables will be reported for the PLS population, AEs will be listed only.

### **9.2.2.10 Pharmacokinetic (PK) assessment(s): Flecainide plasma concentration over time**

PK results will be reported for all evaluable patients in the PK population. For each subject all available flecainide plasma (PK) values are reported in a listing and in a figure. The PK results are reported according to the time the blood sample was collected since initiation of study medication (minutes). If the PK value for the sample taken just before initiation (at  $T_0$ ) is not available or is reported as 'BLQ' (Below Limit of Quantification) the value 0 will be imputed (unless additional information indicates otherwise).

Section 6.2.5.1 indicates the planned time points PK samples are taken.

## FLE-002 (INSTANT) – Final Analysis

## Statistical Analysis Plan

Per cohort per planned PK time point the mean value and standard deviation of the flecainide values are reported in a table and in a figure. These tables and figures can be repeated for specific types of subjects, according to the specific type of conversion to SR (refer to SAP section 3.1, “definition of methods for cardioversion”), these additional analyses will be specified in the overview of TFLs that will accompany the final report.

No PK results will be tabulated for the PLS population, however for these subjects plasma concentrations of flecainide will be presented in listings.

PD results are reported for the PK population.

### Summarizing PK statistics

These results are not planned to be included in the final report. The final report will however show information on  $C_{max}$  and  $t_{max}$ , based on the PK results that are indicated in SAP section 5.5.

Results will be calculated by Eurofins as: 1) per-subject results, and; 2) summary statistics for a selection of subjects. Statistics calculated are: number of observation, mean, standard deviation, coefficient of variance, geometric mean, minimum and maximum. Results will be sent by Eurofins to Sponsor.

Protocol (refer to section 10.2.3 B) additionally indicates reporting of summarizing statistics for PK parameters, which include:

$AUC_{0-10}$ :	The area under the plasma concentration versus time curve from the start of dosing (time zero, $T_0$ ) to 10 minutes post completion of dosing
$AUC_{0-90}$ :	The area under the plasma concentration versus time curve from the start of dosing (time zero, $T_0$ ) to 90 minutes post completion of dosing
$C_{max}$ :	The peak (maximum) plasma concentration prior to the start time of any alternate pharmacological therapy, is to be obtained directly from the plasma concentration time profile
$t_{max}$ :	The time to $C_{max}$ (from the time of start of dosing) is obtained.
$t_{1/2}$ distribution:	The distributive half-life is calculated by the equation $t_{1/2} = \ln(2)/k_{dist}$

